4.3 Evaluations

The patients will initially be seen weekly until stable and then monthly until remission is achieved. They will then be reviewed 2-3 monthly for the rest of the trial depending on clinical need. Prior to entry all patients will have blood sent for hepatitis B

hepatitis C and HIV and have a CT scan of chest abdomen and pelvis to exclude malignancy.

At each clinic visit blood samples will be sent for full blood count, biochemical profile, drug level monitoring and selective proteinuria. Urine samples will be sent for PCR and selective proteinuria.

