4.5 End points

a) Primary Endpoints

Efficacy of MMF in preventing relapse of nephrotic syndrome on withdrawal of tacrolimus therapy. This will be initially measured at 6 months post withdrawal of tacrolimus therapy.

b) Secondary end points

The time to obtaining remission from proteinuria

The degree of remission of proteinuria obtained (complete or partial)

The rate of decline of renal function measured by the MDRD equation for glomerular filtration rate

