4.6 Statistic Analysis

This will be carried out under the direction of [name] -Statistics department Imperial College London. The sample size was based on the main outcome measure, time to relapse, and compared using a 1-sided log rank test assuming a 1% drop-out rate and a 50% relapse free survival rate in the tacrolimus group and a 95% relapse free survival rate in the tacrolimus and MMF group with an alpha level of 0.05 and 80% power. The NCSS PASS package was used. Hintze J (2004) Number Crunching Statistical Systems (PASS). The statistical analysis will be done by using a 1 sided log rank test.

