4.7 Duration

5 years, with 24 months recruitment and 36 months follow up. Primary end points will be analysed when patients obtaining remission for 1 year have stopped tacrolimus therapy for 6 months. Secondary end point analysis of response to treatment will occur when patients have been on treatment for 12 months.

5. Adverse Events and Data Monitoring

It is anticipated that the treatment will be well tolerated as this regime has been extensively used in renal transplant recipients. All adverse events will be actively sort and recorded in the patients' notes. The data and progress of the trial will be reported to and monitored by the West London Renal and Transplant Glomerulonephritis Research Group at Hammersmith Hospital , on a monthly basis (appendix 2).

All Serious Adverse Events (SAE) and Suspected Unexpected Serious Adverse Drug Reactions (SUSADR) will be reported within 24 hours to the committee chairman [name] and to the sponsor, [name], i.e all events irrespective of their relation to study medications, that are either life threatening, result in hospitalization, result in death, result in persistent or significant disability or incapacity . The sponsor will report any such SAE or SUSAR to the regulatory authority in accordance with the European Directive 2001/20/EC.

6. Internal and External Review

The trial has been extensively reviewed, modified and approved by the West London Renal and Transplant Glomerulonephritis Research Group at Hammersmith Hospital. It has been externally reviewed and approved by [name], Professor of Medicine, The Rayne Institute, University College London [name].

Appendix 1
MTAC Trial Overview

Entry
(eligibility criteria)

Randomisation
(16 patients per limb)

Tacrolimus 2mg bd
adjusted to obtain levels of 5-11

MMF 500mg bd
adjusted to obtain levels of 1.5-3.0
and Tacrolimus 2mg bd adjusted to
obtain levels of 5-12ng/L

(treatment for minimum 12months maximum 24 months)

Patients in remission for 12 months

Withdrawal of tacrolimus over 6 months Withdrawal of tacrolimus over 6 months
Stop MMF

Monitor patients for relapse of nephrotic syndrome

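### Visits after remission are not tied to tacrolimus withdrawal and no sample is fixed at the 6-month primary time point, so relapse may be detected late and on a timing that could differ by arm

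*Combined protocol and SAP*

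**What the plan says.** Section 4.5 makes relapse after tacrolimus withdrawal the primary endpoint and says of it: "This will be initially measured at 6 months post withdrawal of tacrolimus therapy". Section 4.7 sets the time of analysis: "Primary end points will be analysed when patients obtaining remission for 1 year have stopped tacrolimus therapy for 6 months". Section 4.6 treats the outcome as time to relapse: "The statistical analysis will be done by using a 1 sided log rank test".

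The visit rule is in section 4.3. Once remission is reached: "They will then be reviewed 2-3 monthly for the rest of the trial depending on clinical need". On urine sampling, the same section says: "Urine samples will be sent for PCR and selective proteinuria".

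No section starts a visit schedule at the beginning of the taper or at the last tacrolimus dose. None requires a sample at month 6 or gives a window around it. None says how to date a relapse found between visits or after month 6, or when to censor a patient without relapse. Blinding and placebo are not mentioned, and section 4.2 titrates MMF to blood levels.

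**The concern.** Relapse is defined by laboratory change, so apart from patients who present with symptoms it is recorded only when someone is seen and sampled. The recorded relapse time is then the date of the next visit. With visits 2 to 3 months apart and not lined up with withdrawal, a patient can relapse before month 6 and still count as relapse-free at the month-6 reading.

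Few events carry the result. On the planning rates, expected relapses are 16 × 0.50 + 16 × 0.05 = 8.8, so one or two relapses read on the wrong side of month 6 matter.

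The interval is also discretionary, and the clinician probably knows the arm. If one arm were seen more often, its relapses would be dated earlier, and the log-rank test would count that as a treatment effect.

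**Working it through.** **1. The plan's own figure.** Inputs from section 4.6: "a 50% relapse free survival rate in the tacrolimus group", "a 95% relapse free survival rate in the tacrolimus and MMF group", one-sided log-rank test, 1% drop-out, "with an alpha level of 0.05 and 80% power".

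- Hazard ratio = ln(0.95)/ln(0.50) = 0.074.
- Freedman events = (1.645 + 0.842)² × [(1 + 0.074)/(1 − 0.074)]² = 8.32.
- Mean event probability = 1 − (0.50 + 0.95)/2 = 0.275.
- Patients = 8.32/0.275 = 30.2; divided by 0.99 = 30.5; so 16 per arm, 32 in all.

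The stated 32 reproduces, and this point does not affect it.

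**2. Share of control relapses not yet seen at month 6.** Assumptions that the protocol does not supply: the 50% applies at 6 months after the last tacrolimus dose (section 4.6 gives no time horizon), the hazard is constant, relapse is found only at routine visits, and all 16 patients per arm reach withdrawal.

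Let g be the months from the last visit to month 6, and S(t) = 0.5^(t/6). Then

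unseen share = [S(6 − g) − S(6)]/[1 − S(6)] = 2^(g/6) − 1.

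For g uniform on (0, w), the average is [6/(w ln 2)] × (2^(w/6) − 1) − 1.

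- w = 2: 4.328 × 0.2599 − 1 = 12.5%, or 1.0 of 8 control relapses.
- w = 3: 2.885 × 0.4142 − 1 = 19.5%, or 1.6 of 8.

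Sensitivity of this share:

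- 0% if a visit falls on month 6 (g = 0).
- 26% (2-monthly) to 41% (3-monthly) if the last visit is a full interval earlier.
- 6% to 9% if the 50% accrues over the 6-month taper plus 6 months.
- 14.5% to 24% if the 50% applies at 12 to 36 months.
- 16% to 25% of the few relapses in the MMF arm, at 95% relapse-free by month 6.

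**3. Power.** Simulated one-sided log-rank test, 16 per arm, 50% versus 95% relapse-free at month 6, 5,000 runs per scenario. Repeat runs differ by about one percentage point.

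| How status is read | 2-monthly | 3-monthly |
|---|---|---|
| Visit on month 6 | 94% | 94% |
| Random phase, censored at month 6 | 90-91% | 87-88% |
| Random phase, censored at last visit before month 6 | 88-89% | 83-84% |
| Random phase, status read at next visit | 96% | 96% |

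The last row exceeds the first because it also counts relapses that occur after month 6.

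At 80% relapse-free on MMF with 3-monthly visits, power is about 57% with a month-6 sample, 44-50% without one, and 60% if the next visit is used.

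The Freedman formula gives lower values throughout: 81.6% for the plan, and 77% (2-monthly) or 74% (3-monthly) when the apparent month-6 rates are put in. It is conservative at so extreme a hazard ratio, so the simulation of the planned test is the better guide.

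**4. Error rate if intervals differed by arm.** No true difference, 50% relapse-free in both arms, nominal one-sided 5%.

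| How status is read | Control 2-monthly, MMF 3-monthly | Control 3-monthly, MMF 2-monthly |
|---|---|---|
| Visit on month 6 | 6-7% | 3% |
| Random phase, censored at month 6 | 8-9% | 3% |
| Random phase, censored at last visit | 5% | 6% |
| Random phase, next visit | about 10% | 2% |

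With equal intervals the error stays near 5%. Reading status at the next visit recovers power but does not protect against unequal intervals.

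**The case against.** A reader might infer that 12-20% of relapses would be missed. The documents do not support that. Review continues at the same interval for the rest of the trial, section 4.2 gives at least 3 years of follow-up, and section 4.5 calls month 6 the initial measurement. Section 4.7 says when analysis happens; it does not tell the analyst to drop a relapse found at the next visit. A relapse that persists is found up to one interval late. The percentage also comes from a model and is not a property of the plan: visits every 2 or every 3 months counted from the last dose would both land on month 6.

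The power loss likewise depends on a censoring rule that the protocol does not state, and it disappears if the next visit is used. Both arguments stand.

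A reader might also infer that detection is biased by arm. That is not shown either. One 2-3 month range applies to both arms, clinical need moves the interval only within it, and section 4.2 stops MMF before the tacrolimus taper, so MMF titration gives no reason for different visit frequency in the relapse window. The split in step 4 assumes that every patient in one arm follows one interval and every patient in the other arm follows the other.

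What remains is that nothing in the plan ensures a month-6 reading, equal intervals, or a single way of dating and censoring. With about nine expected events, these should not be left to be settled after the data are seen.

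**Conclusion.** The point holds as a cheap improvement, not as a flaw that invalidates the trial. The schedule does not guarantee that the primary outcome can be read at its own time point, and the protocol does not settle the dating and censoring on which the result then depends.

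On the step 2 assumptions with random visit phase, 12.5% to 19.5% of control relapses by month 6 are not yet visible then, with 0% to about 41% possible depending on where visits fall. At the planned effect, simulated power stays above the stated 80% on every reading. At a smaller effect it is well below 80% with or without the sample, so the schedule is not the main cause there.

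The 2% to 10% range for one-sided error is conditional on a difference in intervals for which there is no evidence. It supports a common schedule; it does not support a claim that the comparison is biased.

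**What to change.** In section 4.3, set one fixed assessment interval within the existing 2-3 month range, counted from the start of the tacrolimus taper and identical in both arms. Require a urine PCR and serum albumin at 6 months after the last tacrolimus dose, within a stated window (for example ±2 weeks). If the taper lasts its planned 6 months, this point is month 12 from taper start, which both a 2-monthly and a 3-monthly schedule reach (12/2 = 6 visits, 12/3 = 4 visits). The explicit sample covers patients whose taper runs differently.

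In section 4.6, state one rule for dating and censoring by scheduled visit. For example, date a relapse to the scheduled visit at which it is found, assign one found at an unscheduled visit to the next scheduled visit, and say when relapse-free patients are censored. An interval-censored analysis would serve as a sensitivity analysis. With a month-6 sample in place, the alternative censoring choices in step 3 largely coincide.

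The cost is protocol wording, one or two extra routine samples per patient at most, and slightly less scheduling flexibility. Unscheduled visits for care remain allowed, and no treatment changes.

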4.4 Withdrawal and treatment failure

Patients can be withdrawn at patient or physician request. The reason for withdrawal will be recorded in the patients records.

Patients not achieving remission at 1 year will be withdrawn from the trial and alternative treatments considered. They will remain under follow up in the clinic as is current standard practice.

4.5 End points

a) Primary Endpoints

Efficacy of MMF in preventing relapse of nephrotic syndrome on withdrawal of tacrolimus therapy. This will be initially measured at 6 months post withdrawal of tacrolimus therapy.

b) Secondary end points

The time to obtaining remission from proteinuria

The degree of remission of proteinuria obtained (complete or partial)

The rate of decline of renal function measured by the MDRD equation for glomerular filtration rate

4.6 Statistic Analysis

This will be carried out under the direction of [name] -Statistics department Imperial College London. The sample size was based on the main outcome measure, time to relapse, and compared using a 1-sided log rank test assuming a 1% drop-out rate and a 50% relapse free survival rate in the tacrolimus group and a 95% relapse free survival rate in the tacrolimus and MMF group with an alpha level of 0.05 and 80% power. The NCSS PASS package was used. Hintze J (2004) Number Crunching Statistical Systems (PASS). The statistical analysis will be done by using a 1 sided log rank test.

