idiopathic membranous glomerulonephritis diagnosed by renal biopsy. We aim to recruit 32 patients 16 to each arm of the trial.

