4.2 Trial Protocol

The research will be conducted via the glomerulonephritis clinic at Hammersmith Hospital. All patients with significant proteinuria secondary to membranous glomerulonephritis on renal biopsy will be considered for the trial. Patients will be screened for hepatitis B, C and HIV, and undergo CT chest, abdomen and pelvis to exclude viral and malignant causes for their membranous nephropathy (these are the

current standard investigations in all patients with membranous nephropathy.) All patients will be initially treated with maximum tolerated doses of ace inhibitors and angiotensin two antagonists for at least 3 months as is standard current treatment. Patients who remain significantly proteinuric (PCR>100units with hypoalbuminaemia or PCR >300 units with normal serum albumin) despite treatment with maximum tolerated doses of ACE inhibitors and angiotensin two antagonists will be randomised to receive tacrolimus monotherapy or tacrolimus in combination with mycophenylate mofetil therapy. The initial dose of tacrolimus will be 2mg twice a day and this would be titrated to achieve levels of 5-12 ng/ml. The initial dose of mycophenylate mofetil would be 500mg twice a day, and this would be titrated to achieve mycophenolic acid levels of 1.5-3.0 mg/L. Patients with a previous history of tuberculosis, or deemed at high risk due to Asian origin will receive isoniazid 150mg once a day and pyridoxine 50mg once a week.

Treatment will be initially for 1 year. Remission of proteinuria will be defined as complete if urinary PCR <30 units, and partial if urine PCR decreases by >50% but is still above 30 units. Patients not obtaining complete or partial remission after 1 year will be withdrawn from the trial and alternative therapies considered. When patients have been in remission for 12 months on treatment the tacrolimus will be withdrawn over 6 months. Those on MMF and tacrolimus will then have their MMF stopped prior to tacrolimus withdrawal over 6 months. Patients will be offered a renal biopsy prior to withdrawal of therapy. This will help predict relapse and show any evidence of tacrolimus toxicity which may help guide subsequent therapy in the case of relapse. Continuation in the trial is not dependent on undergoing renal biopsy. Patients will be followed for at least 3 years. Patients may withdraw from the trial at any point without any compromise to their clinical care.

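### The 1% drop-out allowance in 4.6 does not cover the patients the protocol itself removes before the primary relapse comparison, so the stated 80% power rests on an unstated share reaching tacrolimus withdrawal

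*Combined protocol and SAP*

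**What the plan says.** Section 4 sets the size at randomisation: "We aim to recruit 32 patients 16 to each arm of the trial". Appendix 1 repeats 16 per limb at the randomisation step.

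Section 4.6 bases that size on time to relapse, compared by a one-sided log-rank test at alpha 0.05 with 80% power, "assuming a 1% drop-out rate and a 50% relapse free survival rate in the tacrolimus group" and 95% in the tacrolimus plus MMF group. It names the software but not the formula, and gives no time point for the two rates.

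Other sections decide who can contribute to that comparison:

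- Section 4.2: "Patients not obtaining complete or partial remission after 1 year will be withdrawn from the trial and alternative therapies considered". Section 4.4 repeats the rule: "Patients not achieving remission at 1 year will be withdrawn from the trial and alternative treatments considered".
- Section 4.2, on those who do remit: "When patients have been in remission for 12 months on treatment the tacrolimus will be withdrawn over 6 months".
- Section 4.5, on the primary endpoint of relapse: "This will be initially measured at 6 months post withdrawal of tacrolimus therapy".
- Section 4.7: "Primary end points will be analysed when patients obtaining remission for 1 year have stopped tacrolimus therapy for 6 months". The timetable there is "5 years, with 24 months recruitment and 36 months follow up".

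No section gives a figure for the share expected to remit by 1 year or to stay in remission for 12 months. The Summary says only that tacrolimus works in most patients and that remissions are often partial. Section 1.1 calls it very effective, without a number.

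**The concern.** A patient can count towards relapse on tacrolimus withdrawal only after passing two steps: remission by 1 year, then 12 months in remission on treatment. Patients who fail either step are lost to the primary comparison by design, not by chance drop-out. An allowance of 1% is 0.01 x 32 = 0.32 of a patient, so 4.6 in effect assumes that every randomised patient passes both steps.

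The 80% power statement is the only justification given for 32. If its loss input does not describe the design, a reader cannot tell how many patients at risk the trial was planned around, or what power it has on the comparison that matters.

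**Working it through.** **Inputs.** 16 per arm (section 4, Appendix 1). One-sided log-rank test, alpha 0.05, 80% power, 50% and 95% relapse-free, 1% drop-out (4.6). Initial assessment 6 months after withdrawal (4.5). The share reaching withdrawal is not in the protocol, so every share below is an assumption.

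**1. The plan's own figure.** Hazard ratio = ln(0.95)/ln(0.50) = 0.074. The one-sided Freedman formula gives (1.645 + 0.842)^2 x (1.074/0.926)^2 = 8.32 events. The average relapse probability is (0.50 + 0.05)/2 = 0.275, so N = 8.32/0.275 = 30.2. Dividing by 0.99 gives 30.5, that is 31, or 32 with equal arms. A continuity-corrected two-proportion formula also gives 16 per arm. So 32 can be reproduced, with essentially all 32 treated as at risk, but the method behind it cannot be identified.

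**2. Does the timetable cause the loss?** A patient remitting at month 12 reaches the assessment at 12 + 12 + 6 + 6 = month 36, which fits the 36 months in 4.7. The loss comes from the two remission steps, not from the end of follow-up.

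**3. Power by share reaching withdrawal.** Simulation of the planned test: 16 randomised per arm, a binomial number reaching withdrawal in each arm, exponential relapse times, rejection if z > 1.645. Two horizons were run, both with 50% and 95% holding at 6 months after withdrawal:

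- Horizon A: every patient censored at 6 months.
- Horizon B: constant hazard, later relapses count, 36 months per patient. A patient remitting at month m has 36 - (m + 12 + 6) = 18 - m months after withdrawal. With m spread evenly over 0 to 12, that is 6 to 18 months.

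| Share reaching withdrawal (assumed) | Expected at risk | Expected relapses by 6 months (x 0.275) | Power, A | Power, B |
|---|---|---|---|---|
| 100% | 32 | 8.8 | 94% | 99% |
| 90% | 28.8 | 7.9 | 91% | 99% |
| 80% | 25.6 | 7.0 | 88% | 98% |
| 70% | 22.4 | 6.2 | 83% | 96% |
| 65% | 20.8 | 5.7 | 80% | 94% |
| 60% | 19.2 | 5.3 | 76% | 93% |
| 50% | 16 | 4.4 | 67% | 87% |
| 40% | 12.8 | 3.5 | 55% | 77% |

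Separate runs agree to about one point. Under A with fixed numbers (tacrolimus/combination), 11/10 gives 82%, 10/11 gives 81% and 10/10 gives 79%, so about 21 at risk is the line. Under B the line lies between 40% and 50%. If patients enter over 24 months and all are followed to month 60, power is 99% at 65%, 96% at 50% and 90% at 40%. Type I error under A, with 50% in both arms, stays between 4.9% and 5.5%.

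**4. Unequal shares under A (tacrolimus/combination).** 60/80% gives 84%, 50/80% gives 81%, 50/70% gives 78% and 80/50% gives 73%.

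**5. Where the share might lie.** Two illustrations fall on either side of the line under A. If 80% remit and 90% of them hold remission, 0.80 x 0.90 = 72% (23.0 of 32). If 80% of them hold it, 0.80 x 0.80 = 64% (20.5 of 32).

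**6. Sensitivity to method.** The Freedman formula is conservative at so extreme a hazard ratio. On it, 80% needs 30.2 at risk, 94.5% of 32, so power drops below 80% once about 5% miss withdrawal. Section 4.6 does not name this formula, and no conclusion here rests on it.

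**The case against.** The strongest reply is that power may well be adequate. Section 4.6 analyses time to relapse by log-rank, not status at 6 months. Section 4.5 says relapse is initially measured at 6 months, which leaves room for later events, and 4.2 follows patients for at least 3 years. On that reading horizon B, or follow-up to month 60, applies, and 80% power survives even if only half the patients reach withdrawal. The text on remission is also encouraging: partial remission counts as success, tacrolimus is described as very effective, and the hypothesis expects a better response with MMF. A higher share in the combination arm can keep power above 80% even under A, as with 50/80%.

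Much of this stands. A reader might infer that the trial is underpowered, or that 80% power requires 65% to reach withdrawal whatever the follow-up. The protocol supports neither: it gives no share, and the 65% line belongs to the 6-month-censored case alone. A reader might also infer that 32 was miscalculated, but step 1 reproduces it.

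The reply does not rescue the 1% input. The favourable case needs 50% and 95% to be 6-month rates, constant hazards and the counting of later relapses, and 4.6 states none of these. If the two rates instead refer to the end of follow-up, or the analysis is fixed at 6 months, the 65% line applies. The statements on remission are not numeric, and a favourable imbalance does not guarantee 80% (50/70% gives 78%).

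**Conclusion.** The concern holds as a mismatch between a design assumption and the design, not as an arithmetic error. The 1% allowance is wrong for a trial that removes non-remitters at 1 year and withdraws tacrolimus only after 12 months in remission. The stated 80% power is therefore conditional on a share that the protocol does not give.

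A shortfall is not proven. Its size depends on that share and on a horizon that 4.6 leaves open: the 80% line is at about 65% reaching withdrawal with censoring at 6 months, and between 40% and 50% with 36 months per patient and constant hazard. All of these figures take the assumed effect (hazard ratio 0.074) as true, and the two lines assume equal shares in the arms. Confidence is high in the mismatch and moderate in the 65% line. The point should be corrected because 4.6 is the only basis given for 32.

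**What to change.** In 4.6:

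1. Replace the 1% allowance with an explicit assumed share of the 32 randomised patients who reach tacrolimus withdrawal after 12 months in remission, given as a range (for example 50-90%, about 16 to 29 at risk).
2. State the time after withdrawal at which 50% and 95% apply, and whether relapses after 6 months count in the log-rank test.
3. Restate the power for the resulting number at risk under that horizon, by simulation of the planned one-sided log-rank test. If the horizon is left open, show both cases: at 90, 80, 70, 65, 60 and 50%, power is 91, 88, 83, 80, 76 and 67% with censoring at 6 months, and 99, 98, 96, 94, 93 and 87% with 36 months per patient and constant hazard.

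The cost is one paragraph. The downside is that the power becomes openly conditional and may fall below 80% at the low end of the range. No extra patients, change of test or change to any treatment rule is requested.
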